In an effort to address this problem, a variety of technologies have been developed to assist with positioning of the cutting blocks and balancing of knee ligaments. One of the newest technologies uses magnetic resonance imaging to create a three-dimentional computer model of the cartilage and bone of a disease knee. A 3-foot standing radiograph determines the mechanical alignment of the limb. The data from these two imaging modalities is combined to determine the ideal position for cutting both the tibia and the femur. The computer model and proposed cut locations are then forwarded in electronic file format for adjustment and approval by the treating surgeon. Because of the varying anatomy of each patient coupled with the unique nature of each patient's osteophyte pattern, patient-specific cutting blocks can then be rapidly manufactured. These cutting blocks sit on the patient's unique anatomical landmarks and position the bone cuts in the optimal locations based on the pre-operative imaging. The cutting blocks are held in place with traditional pins. In the case of an intra-operative discrepancy, the pins can be left in place with the cutting blocks removed and traditional instruments can be used to complete the procedure.

Custom-cutting blocks are touted to have several advantages over traditional instrumentation. With bone cuts being determined by pre-operative imaging, the alignment can be customized to the individual patients. Also, errors in alignment stemming from the intra- and extra-medullary alignment rods are removed. The preservation of the femoral and tibial canals may reduce blood loss in the perioperative period and reduce post-operative hemarthrosis and pain, thereby improving mobility and potentially leading to earlier discharge from hospital. One of the limitations of this new technology is additional cost. The cutting blocks themselves cost \$500 per patient. This is in addition to the cost of the MRI for pre-operative planning. While these costs are significant, if clinical outcome can be improved by either reduced length of stay or avoidance of mal-alignment by 3 degrees, then the cost would be mitigated immediately (in the case of length of stay) or in the long-term (based on reduced need for revision). While several companies currently are under taking similar studies with competitive products, each technique differs from the others and need to be assessed independently.

The purpose of this study is to compare the outcomes between traditional and patients-specific custom cutting blocks using the Smith and Nephew Visionaire system.

Study Objective

Primary objective: To determine if the use of patient-specific custom cutting blocks for implantation of total knee components results in improved limb alignment and component positioning compared to regular instrumentation.

Secondary objectives: To determine if the use of patient-specific custom cutting blocks for implantation of total knee components results in improved knee function as measured by the EuroQol questionnaire, Oxford 12 Knee questionnaire, Pain Catastrophizing Scale, Knee Replacement Expectations Survey, visual analogue scales (VAS) for pain and satisfaction, and the UCLA Activity Level Scale.

Methods

Study design

This is a randomized controlled trial. Patients will be randomized to have their knee implanted using either the patient-specific custom cutting blocks or the regular instrumentation system. Functional and radiographic outcomes will be assessed in a blinded fashion. The Smith and Nephew Legion Primary® total knee system will be used in both groups; this is an implant with a good long term track record based on the GII design {Lidgren, 2004 #334}. The four surgeons participating in this study are [name]; together they form the Concordia Joint Replacement Group. All surgeons have used and are familiar with the regular instrumentation. They will be instructed in the use of the patient-specific custom cutting blocks prior to study initiation. Outcome measures include post operative limb and component alignment, as well as knee functional scores.

Subjects

Inclusion Criteria:

- 1) All patients from the Concordia Joint Replacement Group (CJRG) booked for primary total knee replacement surgery who had agreed to be contacted regarding participation in research. Subjects will be contacted approximately 3-5 months prior to their surgical date to invite them to participate. This will provide adequate time for MRI imaging and production of the custom cutting blocks.

Exclusion Criteria:

- 1) Deformity of the femur preventing use of the intra-medullary guide utilized in the regular instrumentation set.

- 2) Necessity for the use of constrained implants. These types of implants have intra-medullary stems, therefore all bone cuts need to be referenced off intramedullary guides, making image guided bone cuts inappropriate.
- 3) Patients undergoing knee replacement revision surgery. These types of implants also have stems, making the use of image guided bone cuts inappropriate for the same reasons.
- 4) Patients scheduled for bilateral knee surgery (simultaneous or staged)

Procedure

Recruitment:

Potential participants will be identified by our group's research staff from the surgical booking list kept by the Concordia Replacement Group. Permission to review their medical chart for purposes of research and to contact them regarding participation in research will have been obtained using the group's database consent form (HREB approval H2003:004).

Research staff will contact potential participants by telephone approximately 3-5 months before their surgical date to explain the study and ask if they would like to participate. If they agree, they will be sent a cover letter, two copies of the study consent form, and copies of the clinical outcome scores to complete. They will be asked to sign the consent form (if no questions) and complete the questionnaires before meeting with study staff at the pre-anesthetic clinic, who will collate the forms and answer any further questions.

Randomization:

Randomization will occur after enrolment and subjects will be blinded to assignment group. All subjects will be scheduled for and receive the same MRI experience. It is not possible to blind the surgeon to the surgical technique. The block randomization process will be stratified by surgeon to ensure equal distribution between the two surgical techniques.

Surgery:

Anesthetic and surgical technique will be identical for both groups, and will only differ in type of instrumentation used. Patients are normally given an spinal anaesthetic for intra-operative anesthesia. Patients are placed supine with a 5L saline bag beneath the buttock on the operated side and a tourniquet around the thigh. After appropriate prepping and draping, the tourniquet is inflated and a midline skin incision is used, followed by a medial para-patellar arthrotomy. This allows access to the joint for bone cuts using the appropriate instrumentation, soft tissue balancing, and component implantation. To reduce the incidence of infection, all patients are given 1 pre-op and 3 post-op doses of cephazolin or vancomycin (if penicillin allergic), and body exhaust suits are used by all surgical staff in the operating room. As per our group's normal routine, AP and lateral x-rays of the knee are performed in the recovery room to assess for any undetected intra-operative complications (fracture or gross component malposition). These are not the x-rays used for formal assessment of component position – these are done at the 6 month office follow up visit.

Hospital care:

Patient in-hospital care and rehabilitation is standardized using our group's total knee replacement care map. Deep venous prophylaxis consists of sequential compression devices for 24 hours with elastic stockings while in hospital and rivaroxaban for a minimum of 2 weeks post-surgery. Analgesia is obtained oral narcotics and acetaminophen with patient-controlled intravenous analgesia used when necessary.

Follow up:

All patients will follow our group's pre-existing routine follow-up schedule: a fracture clinic visit 2 weeks post-op for surgical staple removal and wound check, a 8 week office visit for clinical, radiological examination and completion of the clinical outcome questionnaires, a 6 month post-op office visit for clinical & radiographic examination and completion of the clinical outcome questionnaires, followed by yearly visits for clinical & radiographic examination and completion outcome questionnaires. For the purposes of this study, data will be gathered until subjects reach two years from surgery.

The only change from our normal clinical follow-up will be at the 8 weeks follow-up radiological examination. A 3 foot standing AP x-ray of the leg will be substituted for the routine AP x-ray of the knee, and a 3 foot lateral x-ray of the leg will be substituted for the lateral knee x-ray. These modified views increase x-rays exposure minimally, while providing proper standardized films for assessment of limb alignment and component alignment {Hewitt, 2001 #206;Jeffery, 1991 #210}.

Special Sub-group follow up:

15 patients from each arm of the study (30 patients in total) will be asked to participate in a CT scan sub-group to assess component rotation. While standardized plain x-rays are good for assessing component alignment in the coronal and saggital planes, CT scans are required to assess component rotation relative to the long axes of the femur and tibia {Jazrawi, 2000 #209;Berger, 1998 #196}. To minimize time commitment from patients, a single CT scan will be undertaken during the hospital stay using a standardized technique {Berger, 1998 #196}. This CT scan is in addition to the plain x-rays as previously described. This sample size of 30 patients was chosen based upon previously published work {Berger, 1998 #196}.

Data storage

Data for this study will be stored in the Concordia Joint Replacement Group's PHIA compliant database (HREB approval H2003:004). Data will be exported to SAS statistical analysis software in a de-identified fashion for statistical analysis.

Outcome Measures

Primary outcome measures:

1. Leg alignment
 - a. Frontal limb alignment as measured on the 3 foot standing film (fig.1-A).

- b. Sagittal limb alignment as measured on the 3 foot lateral film (fig.1-D & E).
- 2. Femoral component position
 - a. Varus/valgus alignment relative to mechanical axis of femur as measured on the 3 foot AP film (fig.1-A).
 - b. Flexion/extension alignment relative to mechanical axis of femur as measured on the 3 foot lateral film (fig.1-D).
 - c. Rotation relative to epicondylar axis as measured by CT scan
- 3. Tibial component position
 - a. Varus/valgus alignment relative to mechanical axis of tibia as measured on the 3 foot AP film (fig.1-C).
 - b. Amount of posterior slope as measured on the 3 foot lateral film (fig.1-E).
 - c. Rotation relative to tibial tubercle as measured by CT scan

[figure not shown]

Figure 1 - Limb Alignment

Secondary outcome measures:

1. EuroQol score at 1 and 2 years
2. Oxford 12 score at 1 and 2 years
3. Pain Catastrophizing Scale score at 1 and 2 years
4. Knee Replacement Expectations score at 1 and 2 years
5. Visual analogue scales (VAS) for pain and satisfaction at 1 and 2 years
6. UCLA Activity Level score at 1 and 2 years.

Miscellaneous measures:

1. Surgical and tourniquet time
2. Number of instrument pans used
3. Length of hospital stay
4. Peri-operative complications such as deep venous thrombosis, pulmonary emboli, wound complications and cardiac events.

Sample Size

This trial is powered to detect a difference in post-operative frontal limb alignment between the two groups. The CJRG have recently had a computer navigation study accepted for publication assessing alignment with the same protocol as outlined in the study. The standard deviation for frontal plane alignment in the traditional instrumentation group was 3.1 degrees. Previous studies have indicated increased risk of early revision with alignment more than 3 degrees from the mechanical axis {Ritter, 1994 #334}. Assuming $p=0.05$ and power of 95%, a sample size of 29 per arm is required. Allowing for 20% drop-out requires 35 subjects per arm total.

Study End Points

The study will end when all enrolled patients are followed out clinically and radiographically to two years. No interim analysis is planned, as this would adversely affect significance testing. The surgeons involved in this study follow their patients closely in the post-operative period; any unforeseen significant complications arising from using the patient-specific custom cutting blocks that cannot be resolved would prompt cessation of the trial. This process is facilitated by the Concordia Joint Replacement Group's weekly planning & post-operative x-ray review rounds.

Analysis

Data for this study will be stored in the Concordia Joint Replacement Group's PHIA compliant database (HREB approval H2003:004). Data will be exported to SAS statistical analysis software in a de-identified fashion for statistical analysis. The two groups will be compared to assess the adequacy of randomization, relevant data will be assessed for normalcy, and the appropriate parametric and non-parametric tests will be used for comparing means and proportions between the two groups. Multiple regression analysis will be used to look for other factors that may affect post operative limb alignment and component position.

Dissemination

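### No MRI eligibility criterion, and randomisation tied only to an undefined enrolment: the plan permits allocating patients whose custom blocks cannot be made, with consequences for treatment in one arm only

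*Combined protocol and SAP*

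**What the plan says.** The protocol's background section explains that the custom technique rests on imaging. An MRI model of the knee is combined with a long standing film, and the blocks are manufactured from the result. Regular instrumentation has no such dependency.

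Under Procedure, Randomization: "Randomization will occur after enrolment and subjects will be blinded to assignment group", and then "All subjects will be scheduled for and receive the same MRI experience". Enrolment is not defined anywhere in the text.

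Under Subjects, the inclusion criterion takes in all of the group's patients booked for primary knee replacement who agreed to research contact. There are four exclusions:
- "Deformity of the femur preventing use of the intra-medullary guide utilized in the regular instrumentation set"
- "Necessity for the use of constrained implants"
- "Patients undergoing knee replacement revision surgery"
- bilateral surgery.

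None mentions MRI.

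On timing, patients are telephoned 3-5 months before surgery, and the reason given is "This will provide adequate time for MRI imaging and production of the custom cutting blocks". Under Recruitment, consent forms are posted after agreement by telephone: "They will be asked to sign the consent form (if no questions) and complete the questionnaires before meeting with study staff at the pre-anesthetic clinic". Staff collect the forms and deal with remaining questions at that clinic. Its date relative to the MRI is not given.

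The Budget section provides 35 sets of blocks, one for each custom-arm patient. A return to traditional instruments is described only for a discrepancy found during surgery. The Analysis section names no analysis population and has no rule for patients who do not receive the allocated instrumentation.

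**The concern.** The exclusions suggest that the authors wanted to randomise only patients suited to both techniques. The first removes patients who could not have the regular technique. The second and third remove patients in whom image-guided cuts are unsuitable because the implants have stems. The step on which the test technique depends, a usable MRI, has no criterion.

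With randomisation tied only to enrolment, nothing in the text prevents allocation before it is known whether blocks can be made. A regular-arm patient without a usable scan can still have the allocated operation. A custom-arm patient cannot, and would either be operated on with regular instruments or leave the comparison. Crossover dilutes the contrast. Dropping such patients from one arm, for reasons that may relate to their knee or general health, means the groups compared are no longer those formed by randomisation. With no analysis population named, either handling is open.

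**Working it through.** **Inputs.** From Sample Size: SD 3.1°, significance level 0.05, power 95%, 29 per arm, 20% drop-out, 35 per arm. Two inputs are inferred. The detectable difference is taken as 3°, which the plan cites as a risk threshold without calling it the target. The test is taken as two-sided.

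**Plan's own figure.** Two-sample t-test, standardised difference 3/3.1 = 0.968, two-sided 0.05, 95% power: n = 28.75, so 29 per arm. This matches the plan, which supports both inferences (a one-sided test needs 24). The stated 35 matches 29 × 1.2 = 34.8.

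**Assumed failure rate.** The documents give none. Let c be the share of custom-arm patients with scan or block failure only, with c from 2% to 10%. Of 35 patients that is 35 × 0.02 = 0.7 to 35 × 0.10 = 3.5. The chance of at least one is 1 − 0.98^35 = 51% at the low end and 1 − 0.90^35 = 97% at the high end.

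**Case A: failures have regular instruments and are analysed as randomised.** They are assumed to gain nothing from the custom technique, so the difference becomes 3 × (1 − c).

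| c | Difference | Power, 28 per arm | Power, 29 per arm | Power, 35 per arm |
|---|---|---|---|---|
| 0% | 3.00° | 94.5% | 95.2% | 97.9% |
| 2% | 2.94° | 93.6% | 94.4% | 97.4% |
| 5% | 2.85° | 92.2% | 93.1% | 96.6% |
| 10% | 2.70° | 89.3% | 90.3% | 94.9% |

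The column for 28 is 35 less 20%. The column for 35 assumes that everyone is analysed.

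**Case B: failures are dropped from the custom arm only.** Starting from 29 against 29, the custom arm becomes 29 × (1 − c):
- c = 2%: 29 against 28.4, power 95.0%
- c = 5%: 29 against 27.6, power 94.7%
- c = 10%: 29 against 26.1, power 94.1%.

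Power barely moves, and the cost is selection. If the dropped patients' mean alignment would have differed from that of the retained patients by D, the custom-arm mean shifts by c × D. For illustration, take D as one SD, 3.1°. The shift is then 0.02 × 3.1 = 0.06° to 0.10 × 3.1 = 0.31°, with no matching shift in the regular arm. D is an assumption, and the trial could not estimate it from patients it had dropped.

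**The case against.** The strongest reply is that this is a gap in wording. Enrolment may well mean that a signed consent form has been received: the call, the posting and the signing all come under Recruitment, before Randomization. Consent pages are not part of the reviewed text and may deal with MRI eligibility. On any assumed rate up to 10% the loss of power is small.

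Much of this stands, and it rules out several stronger readings that a reader might draw:
- *Randomisation comes before consent or MRI.* The text does not say so. The order is unspecified, not shown to be wrong.
- *MRI failures fall only on the custom arm.* Every subject is to be scanned, so inability or refusal can arise in both arms. Only the effect on delivery of the allocated treatment is one-sided.
- *Withdrawals at the clinic add to the imbalance.* Subjects are blinded to allocation, and a patient who withdraws is lost from either arm. The 20% drop-out allowance can already cover such losses, so they are left out of the figures above.
- *A study MRI is done before consent is signed.* The text does not establish this, since forms may be signed before the clinic. It does leave patients with questions no stated route to sign earlier.

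The reply does not dispose of the eligibility gap. As written, the criteria admit patients who cannot be scanned, and enrolment read as signed consent would still not put randomisation after a usable scan. Safety screening at the imaging site would protect the patient but would not keep an already randomised patient in the allocated treatment.

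**Conclusion.** The point holds as a cheap improvement to who is randomised and when. It does not show that the planned sequence is wrong, and it does not challenge the sample size, whose 29 per arm reproduces.

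The plan permits randomising patients who cannot receive the custom technique, and the resulting crossover or exclusion would affect one arm only. With failure assumed at 2-10% and analysis as randomised, power at 29 per arm falls from 95.2% to 94.4-90.3%. If failures are dropped, power stays at 95.0-94.1%, but one arm has been selected after randomisation. That is the main concern, and its size cannot be known in advance. The failure rate, the 3° target, the two-sided test and the assumption that crossover patients gain nothing are not stated in the documents.

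**What to change.** 1. Add to the exclusion criteria: unable to undergo MRI, or no usable planning MRI.
2. Define enrolment and state the order: signed consent received, MRI obtained and confirmed usable for planning, randomisation, then blocks ordered for the custom arm.
3. Reconcile this order with the Recruitment text on the pre-anesthetic clinic, for example by having forms returned and questions answered by telephone before the MRI is booked.
4. State in the Analysis section that any later block failure is analysed in the arm to which the patient was randomised.

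The cost is mainly protocol wording. All subjects are scanned in any case, so no scan is added per randomised patient, and scanning before allocation is compatible with patient blinding. The downsides are an occasional MRI slot used by a patient who is then not randomised, and slightly less time for block production after allocation.

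### Eight unranked primary alignment measures, only one of them powered: with no success rule, the type I error of the primary claim is undetermined

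*Combined protocol and SAP*

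**What the plan says.** - **Objective.** The primary objective asks whether custom blocks give a result that "results in improved limb alignment and component positioning compared to regular instrumentation". It joins two ideas and does not say how they combine.
- **Outcome list.** Under "Primary outcome measures" there are eight angles: two for the leg (1a, 1b), three for the femoral component (2a to 2c) and three for the tibial component (3a to 3c). None is marked as leading.
- **Sample Size.** "This trial is powered to detect a difference in post-operative frontal limb alignment between the two groups". The section gives an SD of 3.1 degrees, 29 per arm and 35 per arm after drop-out, at one significance level: "Assuming $p=0.05$ and power of 95"%. It does not state the difference to be detected. The nearest figure is a threshold from earlier work, "increased risk of early revision with alignment more than 3 degrees from the mechanical axis". The background puts the clinical gain in similar terms, as "avoidance of mal-alignment by 3 degrees".
- **Analysis.** "the appropriate parametric and non-parametric tests will be used for comparing means and proportions between the two groups". The section does not say which of the two applies to which angle. The only comment on protecting significance tests is in Study End Points and concerns interim looks.
- **CT rotation (2c, 3c).** "15 patients from each arm of the study (30 patients in total) will be asked to participate in a CT scan sub-group". That number is attributed to published work, with no power calculation.

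**The concern.** The chance of a false primary claim depends on what counts as success, and the protocol does not say. A report could present a significant tibial slope beside a null frontal alignment as a primary finding without departing from the text. That choice could be made after the results are known.

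The summary of frontal alignment is also open. The rationale is closeness to the mechanical axis, but the sample size fits a difference in means. In a signed mean, varus and valgus errors cancel. Such a test can miss a real gain in accuracy, or be significant when neither arm is closer to the axis.

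**Working it through.** **1. The plan's own figure.** Inputs from Sample Size: SD 3.1, significance level 0.05, power 95%. The difference is taken as 3 degrees, which is inferred. A two-sided two-sample t-test with standardised difference 3/3.1 = 0.968 needs 28.7, so 29 per arm, with power 95.2% at 29. A one-sided test would need 24, so the calculation is two-sided. Drop-out: 29 × 1.2 = 34.8, so 35. The 29 is therefore a sample size for one comparison of mean frontal angle. At 29 per arm, differences of 2.5 and 2 degrees would have power 85.5% and 67.5%.

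**2. Type I error under each possible rule**, with one two-sided 0.05 test per measure:
- Frontal alignment alone decides: 5%.
- All eight must succeed: at most 5%. Power suffers: with 95% power on each and independence, joint power is 0.95^8 = 66%.
- Any one is enough, independent measures: 1 − 0.95^8 = 33.7%.
- Any one is enough, common correlation ρ: 1 − ∫ φ(u) [Φ((1.96 − √ρ·u)/√(1−ρ)) − Φ((−1.96 − √ρ·u)/√(1−ρ))]^8 du. This gives 30.0%, 25.0%, 19.1% and 15.7% at ρ = 0.3, 0.5, 0.7 and 0.8.

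The protocol gives no correlations, so ρ is an assumption. Testing both a mean and a proportion for each angle would raise the any-one figures, and would also take the first rule above 5%.

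**3. Keeping eight co-equal primaries.** Bonferroni gives 0.05/8 = 0.00625 per test. Power for frontal alignment at 29 per arm falls from 95.2% to 79.6%, and 95% would need 43 per arm (t-test).

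**4. Choice of summary.** Simulated trials with 29 per arm and normal angles. All means, and every SD other than 3.1 in the regular arm, are assumptions. Entries are the percentage of trials significant at two-sided 0.05.

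| Regular vs custom arm (mean, SD) | Signed mean, t-test | Absolute deviation, Welch t-test | Proportion beyond 3 degrees, Fisher |
|---|---|---|---|
| (3, 3.1) vs (0, 3.1) | 95% | 45% | 22% |
| (3, 3.1) vs (0, 2.0) | 99% | 98% | 86% |
| (0, 3.1) vs (0, 1.5) | 5% | 93% | 74% |
| (−1.5, 3.1) vs (1.5, 3.1) | 95% | 5% | under 3% |

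The first row can be checked by hand. Mean absolute deviation is σ√(2/π)·exp(−μ²/2σ²) + μ(1 − 2Φ(−μ/σ)). For (0, 3.1) it is 3.1 × 0.798 = 2.47. For (3, 3.1) it is 2.47 × 0.626 + 3 × 0.667 = 3.55. A 3 degree shift in the mean thus becomes a gap of about 1.1 degrees in closeness.

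In the third row the custom arm is more accurate (33% vs 5% beyond 3 degrees), and the signed mean detects it no more often than chance. In the fourth row neither arm is closer to the axis, yet the signed mean is nearly always significant.

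**5. Film visit.** The Surgery section places the x-rays for formal assessment of component position at the 6 month visit. The follow-up text introduces the 3 foot films at 8 weeks, and Table 1 ticks postoperative leg alignment at 8 weeks only.

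**The case against.** The strongest reply is that a lead endpoint exists in practice. Frontal limb alignment is the only powered measure and comes first in the list, and on that reading the error rate is 5%. This largely stands: the protocol points to a lead. It does not designate one, however. A sample size basis neither allocates the significance level nor defines success, and seven other measures keep the primary label.

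A second reply is that nothing in the text says any one angle suffices, and that the word joining the two parts of the objective leans towards requiring both. This also stands. A reader might infer from the eight-item list that the trial runs a false positive risk of about a third. The documents do not support that. The figure needs both an any-one rule that the protocol does not state and independence, which is unlikely for angles from the same limb.

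Third, the protocol never says that the mean is signed, and it plans proportions too. That is correct. The signed mean is one permitted choice, and the fourth row of the table is a constructed case. The point is that the choice is open.

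Fourth, a reader might infer that the 95% power is lost once closeness is the target. The documents do not support that either, because the result turns on the spread in the custom-block arm, which they do not give. If that arm is both re-centred and tighter, power can be as high as planned.

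**Conclusion.** The concern holds as a gap in specification: the protocol leaves the error rate of its primary claim undetermined, which is not the same as showing it to be inflated. It is at most 5% under two of the three plausible rules and about 16% to 34% under the third. That range assumes one test per measure and common correlations from 0.8 to 0.

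The choice of summary is a second open decision with real consequences. For absolute deviation at 29 per arm with means 3 vs 0, power is about 45% if both SDs are 3.1 and about 98% if the custom arm's SD is 2.0. These figures assume normal angles and an inferred 3 degree target. The count of eight, the single powered endpoint and the absence of any rule rest on the text alone. The point should be settled before analysis, and it can be settled by wording. The film visit is a separate inconsistency that affects when the primary outcome is measured.

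**What to change.** 1. Name frontal limb alignment on the 3 foot standing film as the single primary outcome, tested once at two-sided 0.05, and bring the primary objective into line.
2. Make the five other x-ray angles (1b, 2a, 2b, 3a, 3b) secondary with Holm adjustment. Alternatively, test them in a stated fixed order after frontal alignment, each at 0.05, stopping at the first non-significant result.
3. Label the two CT rotation angles exploratory and keep them outside that family.
4. Fix one summary of frontal alignment that measures closeness to the mechanical axis, for example absolute deviation, with the proportion beyond 3 degrees as supportive.
5. State the target difference and the SD assumed in each arm, and restate power for the chosen summary. No added enrolment is proposed.
6. As a separate correction, reconcile the visit for the formal alignment films between the Surgery section, the follow-up text and Table 1.

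**Cost.** The changes are to wording in the objective, outcome list, sample size and analysis sections, plus the visit correction. They need no new data, and the primary test keeps the full 0.05. Component position alone can no longer support a claim of primary success, and the restated power may be below 95%.

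### Four primary component angles (2b, 2c, 3b, 3c) have no target, and the natural reading, a comparison of mean angles, does not measure improved positioning

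*Combined protocol and SAP*

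**What the plan says.** The primary objective (Study Objective) is to find out whether custom blocks give a result that "results in improved limb alignment and component positioning compared to regular instrumentation". The primary outcomes under Outcome Measures include four component angles outside the frontal plane:

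- 2b: "Flexion/extension alignment relative to mechanical axis of femur as measured on the 3 foot lateral film"
- 2c: "Rotation relative to epicondylar axis as measured by CT scan"
- 3b: "Amount of posterior slope as measured on the 3 foot lateral film (fig.1-E")
- 3c: "Rotation relative to tibial tubercle as measured by CT scan"

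Each entry names an axis, a landmark or a film. None gives an intended value, an acceptable range or a better direction. The Analysis section says that "the appropriate parametric and non-parametric tests will be used for comparing means and proportions between the two groups", and sets no cut-off that would turn these angles into proportions.

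On how the custom arm is aimed, the introductory text says: "The computer model and proposed cut locations are then forwarded in electronic file format for adjustment and approval by the treating surgeon". Nothing comparable is written for the regular arm. The two rotation outcomes come only from the CT subgroup of 15 patients per arm (Special Sub-group follow up).

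**The concern.** Improved positioning means lying closer to the intended position. More slope or more flexion is not better or worse in itself, so a difference in mean angle has no direction that can be read as improvement.

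Two errors can follow. First, the introductory text argues for custom blocks because they remove errors from the alignment rods. Removing error reduces scatter, and errors on either side of the target cancel in a mean, so a real gain can go unseen. Second, if the two arms aim at different angles, their means will differ even when both are equally accurate, and the result could be reported as a positioning effect. Because no target is written down, one could also be chosen after the results are known.

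**Working it through.** **Inputs from the document.** SD 3.1 degrees (Sample Size; frontal alignment, traditional instruments). A 3-degree threshold, alpha 0.05, power 95%, 29 per arm (Sample Size). CT subgroup of 15 per arm.

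**Assumptions.** No SD is given for slope, flexion/extension or rotation, so 3.1 degrees is borrowed. Errors are taken as normal and tests as two-sided. The halving of scatter and the differences in aim are illustrations.

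**1. The plan's own figure.** n per arm = 2 × [SD × (z₀.₉₇₅ + z₀.₉₅) / δ]² = 2 × [3.1 × (1.960 + 1.645) / 3]² = 27.75, so 28. The t-test version gives 28.7, so 29, as stated. The sample size was therefore built as a difference of 3 degrees between two mean angles. It covers frontal limb alignment only, but it shows how the authors think of an angle outcome.

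**2. Same target, scatter halved (SD 3.1 against 1.55).** For a normal error centred on the target, mean absolute deviation = SD × √(2/π):

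- Regular arm: 3.1 × 0.798 = 2.47 degrees
- Custom arm: 1.55 × 0.798 = 1.24 degrees
- Share more than 3 degrees off target: 33% against 5%

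Share of trials with p < 0.05 (simulation, 40,000 trials, Welch test for absolute deviation):

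| Measure compared | 29 per arm | 15 per arm |
|---|---|---|
| Mean angle | 5% | 5% |
| Mean absolute deviation | about 90% | about 60% |

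These figures depend on the ratio of the SDs, not on their size. Halving is a favourable case. If scatter falls by a quarter to a third, absolute deviation is significant in about 28% to 49% of trials at 29 per arm, and mean angle stays at 5%.

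**3. Equal scatter, different aims.** Power of the two-sample t-test on mean angle with standardised difference d = (difference in aim) / 3.1:

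| Difference in aim | d | 29 per arm | 15 per arm |
|---|---|---|---|
| 1 degree | 0.32 | 23% | 14% |
| 2 degrees | 0.65 | 68% | 40% |
| 3 degrees | 0.97 | 95% | 73% |

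Both arms have the same mean absolute deviation from their own target (2.47 degrees), so every significant result here occurs without a gain in accuracy. Range for the SD, with aims 2 degrees apart and 29 per arm: 96% at SD 2, 68% at SD 3.1, 47% at SD 4.

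**4. A common target that one arm does not aim for.** Suppose custom plans lie 3 degrees from a protocol-wide target μ away, with mean absolute deviation = SD√(2/π) × exp(−μ²/2SD²) + μ × [1 − 2Φ(−μ/SD)]. With μ = 3 this is 3.55 degrees at SD 3.1 and 3.03 degrees at SD 1.55, against 2.47 in the regular arm. The more precise arm would look worse. This limits which fix is acceptable.

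**The case against.** The strongest reply is that the plan does not say raw angles will be analysed. That is correct. Outcome Measures states what is measured and on which film, and the Analysis section mentions proportions as well as means. A 3-degree limit appears in the introductory text and in Sample Size, so proportions of outliers are conceivable. But that limit refers to the mechanical axis and, in Sample Size, supports frontal alignment. No limit is given for these four angles. A reader might infer that the plan commits to raw means; it is silent, and mean angle is only the most natural reading.

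A reader might also infer that the two arms aim at different angles. The documents do not show this. Both arms use one implant, the same surgeons (stratified randomization) and a technique said to differ only in instrumentation, and the surgeon approves each custom plan. Equally, nothing states that the sagittal and rotational aims are the same, and instrumentation is what sets these angles. The differences in aim above are therefore hypothetical. The loss of sensitivity to scatter does not depend on them.

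For 2b and 2c, neutral to the named axis could be an implied target. It is not written, and 3b and 3c have no obvious zero. Figure 1 and some opening text are not available, and a target could stand there, but no available text points to one.

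Finally, only frontal alignment is powered. That is true, but these four are still listed as primary outcomes.

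**Conclusion.** The point holds as a gap in outcome definition, not as an arithmetic error: the stated 29 per arm reproduces. On its natural reading, the plan's analysis of 2b, 2c, 3b and 3c does not answer the primary question. A halving of scatter would be found at chance level by mean angles, against about 90% (2b and 3b, 29 per arm) or 60% (2c and 3c, 15 per arm) by absolute deviation. The figures for 29 per arm should not be carried over to the rotation outcomes. The risk of a significant result without better accuracy is conditional on a difference in aim that the documents leave open, and its size rests on the borrowed SD. The change should be made before outcome data are compared, because a target chosen afterwards would not be credible.

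**What to change.** For each of 2b, 2c, 3b and 3c, define the outcome as the absolute deviation, in degrees, of the measured angle from an intended value recorded before surgery by the same rule in both arms. Preferably this is the surgeon's intended angle for that patient, written down before allocation is known. A single protocol-wide target is suitable only if surgeons in both arms actually aim for it; otherwise it penalises the arm that does not (step 4 of the working). Compare the deviation between arms and report the raw angles descriptively. The target values are for the investigators to set. Outcome 1b (sagittal limb alignment) also has no target and can be defined in the same amendment.

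The cost is revised outcome wording and one line per angle on a pre-operative form, with no extra patients or imaging. There is some real work. All subjects have the MRI, but no text says a computer plan is made for the regular arm, and pre-operative leg alignment in Table 1 does not supply an intended slope, flexion or rotation. Surgeons must therefore record intended angles for regular-arm patients too. Randomization follows enrolment, and its timing relative to planning is not stated, so the recording step has to be placed before allocation is disclosed.
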